4.1 Inclusion Criteria

4.2 Exclusion Criteria

8 PRESTUDY AND CONCOMITANT THERAPY

9.1.4 Posttreatment Phase (Follow-up)

9.9.4 Potential Risks

11 STATISTICAL METHODS

11.4 Pharmacokinetic Analyses

11.6 Pharmacokinetic/Pharmacodynamic Analyses

11.11 Interim Analysis

REFERENCES

Rationale: Based on recent nonclinical toxicology data from embryo-fetal development studies in rats and rabbits, and fertility and early embryonic development to implantation studies in rats, the inclusion criteria were adjusted to allow women of childbearing potential to participate in the study. Furthermore, serum pregnancy testing was replaced by urine pregnancy testing and the definition of women not of childbearing potential was clarified. Contraceptive requirements for heterosexually active women of childbearing potential were added and details regarding the risk for potential PK drug-drug interaction between ALS-008176 and hormonal contraceptives were provided.

TIME AND EVENTS SCHEDULE

- 1.1 Background
- 4.1 Inclusion Criteria
- 9.7 Safety Evaluations
- 9.9.4 Potential Risks

Rationale: With the availability of the results from embryo-fetal development studies in rats and rabbits, and fertility and early embryonic development to implantation studies in rats, the age limit for participants was lowered to 18 years. The stratification by age was also adjusted to be in line with the lowered age limit for participation in the study.

SYNOPSIS

- 3 STUDY DESIGN AND RATIONALE
- 4 SUBJECT POPULATION
- 5 TREATMENT ALLOCATION AND BLINDING

Rationale: The following changes were made to the endpoints:

- The determination of the RSV RNA viral load area under the curve (AUC) in subjects assigned to a longer dosing duration, if dosing duration is increased by the Independent Data Monitoring Committee (IDMC), was moved from the primary to the secondary endpoints.
- For clarity, the secondary endpoint “Number of hours until peripheral capillary oxygen saturation (SpO₂) ≥93% on room air among subjects who were not on supplemental oxygen prior to current hospitalization” was changed to “Number of hours until peripheral capillary oxygen saturation (SpO₂) ≥93% on room air among subjects who were not on supplemental oxygen prior to the onset of respiratory symptoms”.

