2.1.2. Endpoints

Primary Endpoints

For Part 1:

The primary endpoint is the PK of ALS-008112 and ALS-008144 (and other metabolites, if applicable) in plasma.

For Part 2:

The primary endpoint is RSV RNA viral load (measured by qRT-PCR in the mid-turbinate nasal swab specimens) AUC from immediately prior to first dose of study drug (baseline) until Day 7.

Secondary Endpoints

The secondary endpoints for Part 1 and Part 2 are:

- Safety/tolerability including AEs, physical examinations, vital signs, ECGs, and clinical laboratory results
- RSV clinical course endpoints:
 - Length of hospital stay from admission to discharge and from study treatment initiation to discharge.
 - Length of hospital stay from admission to readiness for discharge and from study treatment initiation to readiness for discharge, with readiness for discharge defined by the investigator.
 - Need for and duration of intensive care unit (ICU) stay.
 - Need for and duration of supplemental oxygen (regardless of method used).

-
- Number of hours until peripheral capillary oxygen saturation (SpO₂) ≥93% on room air among subjects who were not on supplemental oxygen prior to the onset of respiratory symptoms.
 - Respiratory rate, SpO₂, and body temperature return to pre-RSV disease level.
 - Need for and duration of noninvasive ventilator support (eg, continuous positive airway pressure) and/or invasive ventilator support (eg, endotracheal-mechanical ventilation or mechanical ventilation via tracheostomy).
 - Time to return to pre-RSV functional status (Katz ADL score).
 - Need for hydration and feeding by IV catheter/nasogastric tube.
 - Time to clinical stability defined as the time at which the following criteria are all met:
 - normalization of blood oxygen level (return to baseline; by pulse oximetry) without requirement of supplemental oxygen beyond baseline level
 - normalization of oral feeding
 - normalization of respiratory rate
 - normalization of heart rate
 - Improvement on the ordinal scale.
 - All-cause mortality.
 - RSV RNA viral load as measured by qRT-PCR of the mid-turbinate nasal swab specimens which will be used to determine the following:
 - Viral load over time.
 - Peak viral load, time to peak viral load, rate of decline of viral load, and time to RSV RNA being undetectable.
 - Proportion of subjects with undetectable viral load at each time point.

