4. SUBJECT POPULATION

Screening for eligible subjects will be performed as soon as possible following admission to the emergency room or hospitalization, such that subjects are randomized within 5 days of RSV symptom onset. Men or women ≥ 18 years of age (or the legal age of consent in the jurisdiction in which the study is taking place) diagnosed with RSV infection based on a PCR-based diagnostic assay (with or without co-infection with another respiratory pathogen) who have been (or will be) admitted to the hospital and who have signed informed consent will be enrolled. Subjects who were admitted to the hospital for another cause but develop an acute respiratory illness while being hospitalized are also eligible for screening.

The inclusion and exclusion criteria for enrolling subjects in this study are described in the following 2 subsections. If there is a question about the inclusion or exclusion criteria below, the investigator must consult with the appropriate sponsor representative and resolve any issues before enrolling a subject in the study. Waivers are not allowed.

For a discussion of the statistical considerations of subject selection, refer to Section 11.2.

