4.2. EFFICACY

The efficacy analyses include the following primary, secondary and exploratory endpoints.

Primary endpoint

- RSV RNA \log_{10} viral load (measured by qRT-PCR in the mid-turbinate nasal swab specimens) AUC from immediately prior to first dose of study drug (baseline) until Day 7 (or up to 11 days if the dose duration is extended to up to 10 days).

Secondary endpoints

- RSV clinical course endpoints:
 - Length of hospital stay from admission to discharge and from study treatment initiation to discharge.
 - Length of hospital stay from admission to readiness for discharge and from study treatment initiation to readiness for discharge, with readiness for discharge defined by the investigator.
 - Need for and duration of intensive care unit (ICU) stay.
 - Need for and duration of supplemental oxygen (regardless of method used).
 - Number of hours until peripheral capillary oxygen saturation (SpO₂) $\geq 93\%$ on room air among subjects who were not on supplemental oxygen prior to current hospitalization.
 - Respiratory rate, SpO₂, and body temperature return to pre-RSV disease level.
 - Need for and duration of noninvasive ventilator support (eg, continuous positive airway pressure) and/or invasive ventilator support (eg, endotracheal-mechanical ventilation or mechanical ventilation via tracheostomy).
 - Time to return to pre-RSV functional status (Katz ADL score).
 - Need for hydration and feeding by IV catheter/enteral tube.
 - Time to clinical stability defined as the time at which the following criteria are all met:
 - normalization of blood oxygen level (return to baseline; by pulse oximetry) without requirement of supplemental oxygen beyond baseline level
 - normalization of oral feeding
 - normalization of respiratory rate
 - normalization of heart rate

- Improvement on the ordinal scale
- All-cause mortality.
- RSV RNA viral load as measured by qRT-PCR of the mid-turbinate nasal swab specimens which will be used to determine the following:
 - Viral load over time.
 - Peak viral load, time to peak viral load, rate of decline of viral load, and time to RSV RNA viral load being undetectable.
 - Proportion of subjects with undetectable viral load at each time point.
 - RSV RNA viral load AUC from immediately prior to first dose of study drug (baseline) until Day 10 and until Day 14.

Exploratory endpoints

- The amount of:

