
[Time-to-event] (3 separate parameters: overall, invasive, non-invasive)
 
Time to end of supplementation feeding, hydration (hours) [Time-to-event] (2 separate parameters)
	
study drug)/3600, rounded to one decimal
 
The event is defined as the last end date and time of the measured parameter (supplemental oxygen, invasive oxygen, non-invasive oxygen, feeding or hydration). If this date is missing, the end date is considered to be after study completion or withdrawal.
 
Subjects who complete or withdraw from the study prior to the last end date and time of the measured parameter will be censored at the date of completion or withdrawal. If the time is not available they will be censored at 12:00. In case of death prior to the last end date and time of the measured parameter, the time of death will be taken as censoring time (or 12:00 if not available).
 
If no oxygen supplementation, supplemental feeding or hydration was necessary post baseline, the value will be set to 0.

Time point of SpO2 \geq 93% on room air
	
The first time point with SpO2 \geq 93%, where no supplemental oxygen supplementation is given at or after this time point and where no value $<$ 93% are measured after this time point.

Time to SpO2 \geq 93% (hours) on room air [Time-to-event]
	
minimum[date and time of time point with SpO2 \geq 93% on room air, date and time of last SpO2 measurement] - date and time of first dose of study drug)/3600[†], rounded to one decimal
 
Subjects with SpO2$<$93% on room air or who are still on oxygen supplementation at the last SpO2 assessment will be censored at the date and time of the last SpO2 assessment.
 
This parameter will only be calculated for subjects who were not on supplemental oxygen prior to current hospitalization

Time point of return to pre-RSV disease level (hours) for HR, RR, SpO2 (3 separate parameters)
	
The first time point where it is indicated by the investigator that the observed value is normal for the subject, and for none of the time points after this point in time the values are indicated to be abnormal for the subject (separate for HR, RR or SpO2).

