The need and duration of supplemental oxygen will be analyzed by splitting the ITT-i population into two partitions:

- 1) Those patients who require supplemental oxygen before treatment initialization
- 2) Those patients who did not require supplemental oxygen before treatment initialization

Both partitions will be analyzed separately, answering two different questions:

- 1) For those patients who require supplemental oxygen before treatment initiation: Is there a treatment difference in the time to no longer requiring supplemental oxygen? This analysis will be performed primarily with a Kaplan-Meier analysis and a stratified Gehan test.
- 2) For those patients who did not require supplemental oxygen before treatment initialization: Is there a treatment difference in preventing the use of supplemental oxygen? This partition will be analyzed using a stratified (exact) logistic regression model as specified above.

While we cannot integrate these results they are conceptually linked. We will combine the p-values for both independent tests for the comparison of each active group versus placebo using the method of Liptak^[3].

In addition to the analysis described above, the time to no longer requiring supplemental O₂ will be analyzed on the total group of subjects where subjects who do not require supplemental oxygen during the study are considered to have their event at time 0. As before, this will be analyzed in an exploratory sense using Kaplan-Meier analysis and with a stratified Gehan test to test for treatment differences.

This analysis will be repeated by method of administration (invasive, non-invasive).

The analysis for the need and duration of supplemental feeding and supplemental hydration will be done in similar fashion as for supplemental oxygen use described above.

Time to SpO₂ ≥ 93% (hours) on room air

Time to SpO₂ ≥ 93% (hours) on room air will be summarized and listed for subjects who were not on supplemental oxygen prior to current hospitalization.

Among subjects who were not on supplemental oxygen prior to current hospitalization, the time to SpO₂ ≥ 93% (hours) on room air, will be summarized and analyzed in an exploratory sense using Kaplan-Meier analysis.

The time from first dose to SpO₂ ≥ 93% (hours) on room air will also be analyzed using AFT methodology.

Time to return to pre-RSV disease level (hours) for RR, SpO₂; body temperature

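### The SAP and the current protocol define the population for time to SpO2 ≥93% on room air by different reference times: hospital admission in the SAP, onset of respiratory symptoms in the protocol

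*SAP*

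**What the plan says.** The protocol defines this secondary endpoint twice, in the synopsis and in section 2.1.2, with the same restriction: "on room air among subjects who were not on supplemental oxygen prior to the onset of respiratory symptoms".

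The SAP uses a different restriction in each section where the endpoint appears:

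- Section 4.2 (list of secondary endpoints): "on room air among subjects who were not on supplemental oxygen prior to current hospitalization".
- Section 4.2.4.1, Table 1 (derivation): "This parameter will only be calculated for subjects who were not on supplemental oxygen prior to current hospitalization".
- Section 4.2.4.2 (analysis methods): the endpoint "will be summarized and listed for subjects who were not on supplemental oxygen prior to current hospitalization". The next sentence there applies the same restriction to the Kaplan-Meier analysis.

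The SAP never uses the symptom-onset wording for this endpoint and gives no reason for departing from it. Its introduction says that it should be read together with the protocol. It does not say that its own definitions take precedence.

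**The concern.** The entry in Table 1 is an operative rule: it tells the programmer for whom the variable exists at all. A programmer who follows it will build a population that the protocol does not define, and the study report would then present an endpoint named in the protocol for a different set of patients.

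The choice of reference time has a purpose. The restriction appears meant to select patients whose need for oxygen arose with the RSV illness, so that reaching 93% on room air means recovery from that illness. Onset of symptoms marks the start of the illness. Admission may come later or, for patients already in hospital, earlier. Related SAP endpoints, such as return of SpO2 to its pre-RSV level, are also tied to the state before the illness and not to admission.

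**Working it through.** No figure is at issue, so the check compares texts and then asks whether the two reference times can separate under the eligibility rules.

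**Step 1: can symptom onset come before admission?** Yes. Protocol section 4 requires that "subjects are randomized within 5 days of RSV symptom onset", which leaves room for oxygen to be started after onset and before admission. Inclusion criterion 2 also allows randomization in the emergency room before hospitalization. The documents do not say whether emergency-room time counts as hospitalization. If it does not, oxygen started there also falls before admission.

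**Step 2: can admission come before symptom onset?** Yes. Protocol section 4 makes patients eligible for screening if they were admitted for something else and developed an acute respiratory illness in hospital. Such a patient may have been given oxygen after admission but before any respiratory symptom.

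**Step 3: classify each oxygen history under both rules.**

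| Oxygen history | Protocol rule | SAP rule |
|---|---|---|
| None before onset and none before admission | in | in |
| On oxygen before both (for example, long-term home oxygen) | out | out |
| (a) Started after symptom onset, before admission | in | out |
| (b) Admitted for another cause, none before admission, started in hospital before respiratory symptoms | out | in |

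The rules agree in the first two rows and disagree in the last two.

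**Step 4: how large are (a) and (b)?** The documents contain nothing from which to estimate this. Neither group can be shown to be empty or large.

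**Step 5: what does the difference touch?** The endpoint is analysed by Kaplan-Meier methods, described as exploratory, and by an accelerated failure time model (SAP 4.2.4.2). Its population therefore feeds into reported curves and acceleration factors. The primary analysis in SAP 4.2.3 and the sample size and error control in SAP 1.4 and 4.2.1.1 do not use it.

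**Step 6: where does the difference come from?** The protocol's amendment list shows that Amendment 2 replaced the admission wording with the symptom-onset wording. The SAP carries other text that does not match the current protocol: a lower age limit of 50 years against 18, and a first interim analysis at 45 randomized against 45 having completed treatment. The likeliest explanation is that the SAP was not brought up to date. The finding does not depend on that history, because the current protocol text and the SAP text conflict as they stand.

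**The case against.** The strongest reply is that the two wordings were meant to describe much the same patients. The Amendment 2 entry introduces the change with "For clarity, the secondary endpoint", which presents it as a clarification and not as a new population. That is a fair reason to expect large overlap. It does not settle the matter, because the literal rules differ and the SAP retains the wording that the sponsor chose to replace.

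A second reply is that little depends on it. This is one of many secondary endpoints. Patients left out here still contribute to other oxygen analyses, namely time to no longer requiring oxygen in the total group, return to pre-RSV SpO2 and time to clinical stability. This stands, and it is why the point is minor.

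Some stronger readings are tempting but not supported:

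- **That the endpoint is analysed in the wrong patients generally.** Only groups (a) and (b) are affected.
- **That a set number of the 90 planned patients is wrongly left out.** Any such number needs an assumed percentage for which the documents give no basis. Efficacy is also analysed in the infected intention-to-treat set, not in all randomized patients.
- **That every patient on oxygen in hospital before RSV symptoms is wrongly kept in.** A home-oxygen user admitted for another cause is excluded by both rules. The protocol also speaks of respiratory symptoms, not RSV symptoms, so a patient given oxygen for another respiratory illness might be kept by its rule too.
- **That the SAP adds patients who cannot reach the event.** Those in (b) had no oxygen before admission, and nothing in the documents says they cannot recover. Patients who have not recovered are censored at their last SpO2 assessment.

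**Conclusion.** The mismatch is real but limited. The SAP and the current protocol give different populations for time to SpO2 ≥93% on room air, and they classify groups (a) and (b) in opposite ways. The size of the effect is unknown and could be small.

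A reader might infer that the treatment comparison is biased. The documents do not support that: both restrictions rest on status before treatment, so neither by itself favours an arm. What changes is the set of patients the estimate describes. The primary endpoint, power and type I error are unaffected.

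This rests on reading both restrictions literally and on taking the current protocol text as the sponsor's intended definition, since the SAP offers no reason to depart from it.

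**What to change.** In SAP 4.2, in the Table 1 entry for time to SpO2 ≥93%, and in both sentences of 4.2.4.2, replace the restriction to patients "who were not on supplemental oxygen prior to current hospitalization" with the protocol's "among subjects who were not on supplemental oxygen prior to the onset of respiratory symptoms". Do this before unblinding. If the sponsor prefers the admission-based population, the SAP should say so and give the reason.

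The cost is SAP wording and the matching line of derivation code. The data should allow it. Protocol section 8 calls for therapies in the 7 days before first dose to be recorded and lists home oxygen among the therapies to capture. Onset is at most 5 days before randomization and the first dose follows within 4 hours, so the recording period reaches back past onset by at least 7 days − (5 days + 4 hours) = 44 hours. That margin would disappear if the monitoring committee widened the onset window to 7 days, as protocol section 11.12 allows. The sponsor should also confirm that oxygen start dates and times are captured.

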8. PRESTUDY AND CONCOMITANT THERAPY

Prestudy therapies administered up to 7 days before first dose of study drug must be recorded at screening.

All subjects will receive supportive care according to local institution standard. While treatment guidelines and standards vary based on local practice and should be considered in the management of subjects, within the parameters of this study, it is recommended that supplemental oxygen can be administered or withdrawn, as appropriate to maintain an SpO₂ ≥93% (for subjects whose baseline SpO₂ is ≥93% when clinically stable).

Concomitant therapies must be recorded throughout the study beginning with start of the first dose of study drug to the Day 28 visit (±2 days). During hospitalization, concomitant medication will be recorded by the site staff in the eCRF. Upon discharge, subjects will be required to document use of concomitant medication in the electronic device in a medication log, which will serve as basis for recording the concomitant medication in the eCRF by the site staff.

Concomitant therapies should also be recorded beyond Day 28 in the subject's medical notes and reported by SAE forms (if applicable) only in conjunction with SAEs that meet the criteria outlined in Section 12.3.2.

All therapies (prescription or over-the-counter medications, including vaccines, vitamins, herbal supplements, home oxygen therapy; non-pharmacologic therapies such as electrical stimulation, acupuncture, special diets, exercise regimens) different from the study drug must be recorded in the eCRF. Recorded information will include a description of the type of the drug/therapy, treatment phase, the dose regimen, route of administration, and its indication. Modification of an effective preexisting chronic therapy should not be made for the explicit purpose of entering a subject into the study, however if a subject has received acute doses of a prohibited drug, switching to an alternative drug chosen at the discretion of the investigator is allowed.

Concomitant medications are permitted as indicated for the management of study subjects with the exception of the medications noted here. The following medications are not permitted during the study and for the time period prior to randomization as noted:

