11.3. Efficacy Analyses

Primary Endpoint

For Part 2, the primary endpoint in this study is RSV RNA log₁₀ viral load (measured by qRT-PCR in the mid-turbinate nasal swab specimens) AUC immediately prior to first dose of study drug (baseline) over 7 days. Mean log₁₀ viral load values over time will be analyzed using a restricted maximum likelihood based repeated measures approach. Analyses will include the fixed, categorical effects of treatment, strata, visit, and treatment-by-visit interaction, as well as the continuous, fixed covariates of baseline log₁₀ viral load and baseline log₁₀ viral load by-visit interaction. An unstructured (co)variance structure will be used to model the within-subject errors over time. The differences in the AUCs for active versus placebo will be derived using

appropriate contrasts deriving least square mean differences, including the 95% 2-sided confidence intervals. For inferential purposes, p-values will be compared with significance levels controlling for the (family-wise) type 1 error rate. Details will be provided in the SAP that will be finalized before the first formal interim analysis of Part 2.

Secondary Endpoints

The secondary endpoint of time to clinical stability is defined as the time at which the following criteria are all met:

- normalization of blood oxygen level (return to baseline, pulse oximetry) without requirement of supplemental oxygen beyond baseline level
- normalization of oral feeding
- normalization of respiratory rate
- normalization of heart rate

Normalization criteria will be specified in the SAP. Subjects for which no time point could be established (eg, withdrawal of informed consent before reaching the endpoint or no clinical stability at last observation) will be (right-) censored at the latest time point at which it could be established that clinical stability was not reached. The differences in time to clinical stability of active dose regimens versus placebo treatment will be estimated using a Cox proportional hazard model; as baseline covariates, stratification factors, absence/presence of other viral or bacterial infections, baseline \log_{10} viral load, and time from onset of first symptoms to treatment will be added. Treatment effect versus placebo will be reported, including 95% confidence intervals. In case the proportional hazards assumption is not satisfied, appropriate sensitivity analyses will be performed as detailed in the SAP.

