
Time to return to pre-RSV disease level (hours) for HR, RR, SpO2 [Time-to-event]
	
(minimum[date and time of time point of return to pre-RSV disease level, date and time of last measurement] - date and time of first dose of study drug)/3600, rounded to one decimal
 
If none of the values are indicated to be abnormal for the subject, this value will be set at time 0.
 
Subjects with an abnormal value at the last assessment will be censored. Subjects for which this last assessment is the baseline

	assessment will be censored at time 0.
Time to return to pre-RSV disease feeding status (hours) [Time-to-event]	
(Date and time of event or censoring - date and time of first dose of study drug)/3600, rounded to one decimal
 
All subjects are assumed to have no supplemental feeding pre-RSV.
 
The event is defined as the last available end date and time supplemental feeding was provided. If this date is missing, the end date is considered to be after study completion or withdrawal
 
Subjects who complete or withdraw from the study prior to the event will be censored at the date of completion or withdrawal. If the time is not available they will be censored at 12:00. In case of death prior to an event the time of death will be taken as censoring time (or 12:00 if not available).
 
If no supplemental feeding was necessary post baseline, the value will be set to 0.

Time to Clinical Stability [Time-to-event]	
maximum[time to return to pre-RSV disease level for SpO₂, RR and HR, feeding]
 
Subject will be censored if the subject is censored for at least 1 of the 4 time to parameters at the minimum of the available data. If no data are available the time will be censored at 0 hours.

Time point of return to normal temperature (hours) [Time-to-event]	
All subjects are assumed to have a normal temperature level pre-RSV disease
 
Time point of return to pre-RSV disease level temperature is defined as the first time point with a normal temperature and no time points after that time point with an abnormal value.
 
The normal limits to be used are:
 
 - Axillary: 36.1 – 38.0 - Forhead: 36.1 – 38.0

	
 - Oral: 36.1 – 38.0 - Rectal: ≤ 37.2 - Tympanic: ≤ 37.8 
If there were no abnormal values post baseline, the value will be set at 0 hours.

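### Time to clinical stability: the SAP's Table 1 derivation leaves out the no-extra-oxygen condition that belongs to the endpoint definition

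*SAP*

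**What the plan says.** **Definition.** Protocol 11.3 lists four criteria that must all be met. The oxygen criterion reads "normalization of blood oxygen level (return to baseline, pulse oximetry) without requirement of supplemental oxygen beyond baseline level". SAP 4.2 repeats it almost word for word: "normalization of blood oxygen level (return to baseline; by pulse oximetry) without requirement of supplemental oxygen beyond baseline level". On the detail, Protocol 11.3 adds: "Normalization criteria will be specified in the SAP".

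**Derivation.** SAP 4.2.4.1, Table 1, turns this into "maximum[time to return to pre-RSV disease level for SpO₂, RR and HR, feeding". For SpO2, as for heart rate and respiratory rate, the component time is "The first time point where it is indicated by the investigator that the observed value is normal for the subject", with no abnormal marking afterwards. Two further Table 1 rules matter:
- The component is set to time 0 if no value was ever marked abnormal.
- The composite is censored only if at least one of the four components is censored.

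**Neighbouring rows.** The row for SpO2 of at least 93% on room air states a no-oxygen condition and censors subjects still on oxygen at the last assessment. Time to end of oxygen supplementation is derived separately and is not fed into clinical stability.

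**Oxygen in the trial.** Protocol Section 8 recommends that "supplemental oxygen can be administered or withdrawn, as appropriate to maintain an" SpO2 of at least 93%, for subjects whose stable saturation is at that level.

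**The concern.** Oxygen is given in order to bring saturation up. A normal reading on oxygen is therefore an ordinary state for a treated patient who has not yet recovered, and the second half of the definition is there to exclude it. Without that half, the composite can call a subject stable while the subject still needs more oxygen than at baseline.

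Time to clinical stability is a named secondary objective. SAP 2.3 selects it for supportive analysis on the per-protocol and ITT sets, and SAP 4.6 relates it to viral load AUC. If Table 1 is programmed as it stands, the reported endpoint differs from the one the protocol defines, and a correction after unblinding would be post hoc.

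**Working it through.** The documents give no event rate, median or power for this endpoint, so there is no plan figure to reproduce. The check is a comparison of texts, followed by one hand calculation.

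**1. Does oxygen enter any component?**

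| Component | Table 1 event | Oxygen term |
|---|---|---|
| SpO2 | investigator marks the value normal, none abnormal later | none |
| Respiratory rate | same rule | none |
| Heart rate | same rule | none |
| Feeding | last end of supplemental feeding | none |

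**2. Does another rule restore it?** No. The censoring rule refers only to these four components. The time-0 rule for SpO2 applies whatever the oxygen use. SAP 4.2.4.2 refers to clinical stability only to assign an analysis method.

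**3. Hand calculation.** Assumed subject: SpO2 marked normal from 0 h while on oxygen above baseline level, respiratory rate and heart rate normal at 24 h, no supplemental feeding (0 h), extra oxygen stopped at 96 h.

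- Table 1: max(SpO2, RR, HR, feeding) = max(0, 24, 24, 0) = 24 h.
- With the oxygen condition: max(0, 24, 24, 0, 96) = 96 h.
- Oxygen never stopped: Table 1 still gives an event at 24 h. Under the definition there is no event and the subject is censored.

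**4. Illustrative simulation.** Every input here is assumed; none comes from the documents. Component times are independent lognormals with log-SD 0.7. Medians are 48 h for respiratory rate, 36 h for heart rate and 96 h for oxygen among users. 60% of subjects are on oxygen, and the active arm has oxygen time multiplied by 0.7 with nothing else changed.

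| Marking of SpO2 while on oxygen | Definition, median placebo vs active | Table 1, median placebo vs active |
|---|---|---|
| always normal | 90 vs 79 h | about 62 h in both arms |
| abnormal until oxygen ends in half of users | 90 vs 79 h | about 74 vs 70 h |

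In the first row about 41% of placebo subjects are scored stable while still on oxygen. With log-SD from 0.4 to 0.8 that share runs from about 52% down to 39%. The result turns on how investigators mark readings taken on oxygen, which the documents do not say.

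**The case against.** - **Delegation.** Protocol 11.3 leaves the normalization criteria to the SAP. That allows the SAP to say what counts as normal. It does not cover removing a condition written into the definition, which SAP 4.2 itself repeats.
- **The investigator's judgement.** The input is a marking of normal for the subject, not a bare saturation value, so an investigator may allow for oxygen. The eCRF completion guidelines named in Protocol Section 15 might say so, but they are not available here. This stands as a limit: a reader might infer that oxygen is ignored in practice, and the documents do not show that. They show that the derivation does not enforce the condition.
- **An oxygen effect could never show.** A reader might infer this from the simulation. It holds only if every on-oxygen reading is marked normal. Under Table 1 any later abnormal marking delays the event, and the second simulation row then shows a difference between arms.
- **The stand-alone SpO2 endpoint.** A reader might infer that time to return to pre-RSV level for SpO2 has the same fault. Protocol 2.1.2 attaches no oxygen condition to that endpoint, so nothing was dropped there.
- **Meaning of baseline.** SAP 2.1 defines the baseline record as the last before first intake, while Protocol Section 8 speaks of saturation when clinically stable. On the first reading, a subject on unchanged oxygen since enrolment is not above baseline. This objection stands, and the text needs to settle it.
- **Oxygen is analysed elsewhere.** Duration of oxygen, time to its end, room-air SpO2 and the ordinal scale all reflect oxygen need. They limit the damage but do not repair this composite.

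**Conclusion.** Wrong as written, and should be fixed. The SAP contradicts both the protocol and its own Section 4.2: the condition "without requirement of supplemental oxygen beyond baseline level" is part of the endpoint but enters neither the event nor the censoring rule in Table 1. Coded literally, a subject on oxygen above baseline level whose SpO2 is marked normal becomes stable once respiratory rate, heart rate and feeding are normal. In the assumed example that is 72 h early (96 − 24), and an event replaces a censored time if oxygen never stops.

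That the derivation permits this follows from the text alone. How often it would happen depends on the share of subjects on extra oxygen and on how their readings are marked. Neither is given, so the size and direction of any effect on the treatment comparison cannot be stated. The point concerns one secondary endpoint. The primary analysis, its alpha and the sample size are unaffected.

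**What to change.** Change Table 1 for Time to Clinical Stability only:

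1. Add a fifth term to the maximum: time from first dose to the end of supplemental oxygen or ventilator support above baseline level, set to 0 if none was given after first dose.
2. Censor the composite if this term is censored, and change 4 to 5 in the censoring rule.
3. State whether baseline level means the pre-RSV level or the level at the baseline record.
4. Clarify the censoring time. Table 1 refers to the minimum of the available data. If that covers all components, a never-weaned subject with SpO2 time 0 would be censored at 0 h, whereas Protocol 11.3 censors at the latest time known not to be stable.

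A separate fifth term is needed. If an oxygen clause were only added to the SpO2 row, the time-0 rule could still set that component to 0 for a subject never marked abnormal. The existing time to end of oxygen supplementation cannot be used unchanged, because it counts any oxygen rather than oxygen above baseline level. Leave the stand-alone SpO2 return-to-pre-RSV endpoint as it is.

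The cost is SAP wording, one new derived variable and a changed censoring rule. Oxygen type, duration and amount are already collected (Protocol 9.2). The change should be made before database lock and unblinding.
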